#### **Limitations:**

- Obesity is a well-known chronic condition of increased intraabdominal pressure, but a baseline measure is provided and acute variations will be investigated, therefore minimizing this potential bias
- All the measurements except for urine collection are assessed during surgery and perioperatively, so eventual late variation may be missed, despite sought homeostasis responses are thought to operate in rapid circumstances

### 3.5 Primary safety endpoints

- The study should be stopped if the patients experience any symptoms or complications due to the interventions implemented.
- The need of opioid will be assessed by the pain score scale and will be restricted to the minimum level required to control the patient's pain and to

provide optimal comfort, as opioid administration may be a confounding element in vasopressin release

- All the measurements will pose minimal risk to the patient. ONSD assessment is non-invasive and safe. Urine collection is routinely assessed during Sleeve Gastrectomy by means of a Foley catheter. Blood draws pose only minimal risk to the patient. Urine output is measured every shift per the nursing staff as standard of care.
- Variations in PEEP level are currently performed during general anesthesia, especially in obese patients and during laparoscopy; according to this study design are supposed to be transient and controlled, therefore not potentially dangerous to patient's intra- and post-operative ventilation

#### **4. SUBJECT SELECTION AND WITHDRAWAL**

##### **4.1 Inclusion criteria**

- Patients scheduled for Sleeve Gastrectomy will be eligible

##### **4.2 Exclusion criteria**

- Age below 18 years
- American Society of Anesthesiologist (ASA) class IV or V
- Other evident/diagnosed causes of increased IAP or increased intrathoracic pressure, except for obesity
- Previous or concomitant neurological disease
- Previous or concomitant ophthalmic conditions/eye surgery
- Previous or concomitant lung diseases
- Patient refused to have a Foley catheter placed

### **4.3 Subject recruitment and screening.**

Patients scheduled for elective Sleeve Gastrectomy, according to bariatric surgery eligibility criteria, will be recruited from the General Surgery outpatient department at Cleveland Clinic Florida.

### **4.4 Early withdrawal of subjects**

Patients may withdraw from the trial at any time and for any reason. Some possible reasons of withdrawal include the following:

- Development of any medical condition or need for concomitant treatment that precludes further participation in the trial.
- Unacceptable adverse event due to the suggested study interventions.
- The investigator removes the patient from the trial in the best interest of the patient.
- Patient withdraws consent to continued participation in the trial.

## **5. STATISTICAL PLAN**

This is the sample size calculation for identifying significant increase in vasopressin release after an elevation in intra-abdominal pressure.

Study Design:

Patients undergoing a Sleeve Gastrectomy are to be enrolled to participate in the study. 4 different conditions in which the measurements should be done during and after the surgery:

A) Baseline

- B) 10-15 minutes after insufflation
- C) 10-15 minutes after stabilization
- D) 10-15 minutes after desufflation

Primary aim:

Expecting 20-25% increase in the normal value of vasopressin significant for the study purpose.

Assumptions:

- The normal range value of vasopressin is from 1 to 4pg/ml. According to the number stated in the reference articles, we assume the coefficient of variation is 0.455.
- The type I error rate for the overall test comparing the three groups will be 0.05.
- There would be six pairwise group comparisons: A vs B, A vs C, A vs D, B vs C, B vs D, C vs D; the type I error rate for each comparison will be 0.0083(Bonferroni correction) and the data were assumed to be log-normal distributed.
- Power was computed based on 80%.

Statistical Method:

Repeated measures ANOVA is used to compare the means score of vasopressin across four different conditions. The comparison between any two conditions is accessed using paired t-test. To adjust for the multiple test problem, Bonferroni correction is applied and the type I error rate for each comparison will be 0.0083.

Result:

Plausible sample size for any two conditions comparison with 25% vasopressin increase should be 57

9

V 4 , 2018 01/16/2019 NCT Number: NCT03707054

---

Table 1. Sample Size Calculation			
Increase Rate	Nominal Power	Actual Power	N
20%	0.8	0.802	83
20%	0.9	0.900	104
25%	0.8	0.806	57
25%	0.9	0.902	71
30%	0.8	0.803	42
30%	0.9	0.907	53

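### Holm's step-down on the same six paired t-tests would give more power per comparison than flat Bonferroni at 0.0083, with the same 0.05 family-wise bound

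*Combined protocol and SAP*

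**What the plan says.** Everything on this point is in Section 5 (Statistical Plan).

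- **Design:** "4 different conditions in which the measurements should be done during and after the surgery", labelled A to D.
- **Overall test:** under Statistical Method, "Repeated measures ANOVA is used to compare the means score of vasopressin across four different conditions". Under Assumptions, however, "The type I error rate for the overall test comparing the three groups will be 0.05".
- **Pairwise family:** "There would be six pairwise group comparisons: A vs B, A vs C, A vs D, B vs C, B vs D, C vs D".
- **Pairwise test:** "The comparison between any two conditions is accessed using paired t-test".
- **Multiplicity:** "Bonferroni correction is applied and the type I error rate for each comparison will be 0.0083". No step-down, closed or gated procedure is mentioned.
- **Sample size:** "the data were assumed to be log-normal distributed" and "we assume the coefficient of variation is 0.455". Table 1 gives N = 57 (actual power 0.806) for a 25% increase in any one pairwise comparison at nominal 80% power.

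**The concern.** Single-step Bonferroni holds every one of the six tests at 0.05/6, even after some of the six null hypotheses have been rejected. Holm's procedure orders the p-values and compares the smallest with 0.05/6, the next with 0.05/5, and so on to 0.05/1, stopping at the first failure. It controls the family-wise error strongly at 0.05 under any dependence between the tests, so it needs no assumption that Bonferroni does not. Each threshold is at least 0.05/6, so it can only add rejections.

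What is at stake is some power on individual comparisons at no cost in patients. The gain matters most when several conditions truly differ, which is what the expected results in Section 3.4 describe: vasopressin raised at B and C, lower at A and D.

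The mention of three groups also sits badly with four conditions and six pairs, so it is worth checking which number the calculations use.

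**Working it through.** **Inputs from Section 5.** Four conditions; six pairs; per-comparison alpha 0.0083; paired t-test; log-normal data; coefficient of variation (CV) 0.455; 25% increase; N = 57.

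**Assumptions not in the documents.** Two-sided tests on log values; equal variances; and one common within-patient correlation, back-solved from Table 1 as 0.4 on the original scale.

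**Step 1: which number of conditions was used.** Four conditions give 4 × 3 / 2 = 6 pairs and 0.05/6 = 0.0083. Three groups would give 3 pairs and 0.05/3 = 0.0167. The plan's alpha therefore already uses four.

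**Step 2: reproduce the plan's N.**
- Log-scale SD = √ln(1 + 0.455²) = √0.188 = 0.434.
- Log-scale correlation = ln(1 + 0.4 × 0.455²) / 0.188 = 0.423.
- SD of the log difference = 0.434 × √(2 × (1 − 0.423)) = 0.466.
- Effect = ln 1.25 = 0.223.
- Noncentrality = (0.223 / 0.466) × √57 = 3.61; two-sided critical t at 0.0083 with 56 degrees of freedom = 2.74.
- Power from the noncentral t = 0.806, as in Table 1.

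The same inputs reproduce all six rows: N = 83, 104, 57, 71, 42, 53 with power 0.802, 0.900, 0.806, 0.902, 0.803, 0.907. So 57 patients do give the planned power for one pair at 0.0083.

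**Step 3: Bonferroni against Holm at N = 57.** The table comes from 40,000 simulated trials per pattern. Power is per true 25% difference. The last two columns give family-wise error as Bonferroni / Holm, and the chance of at least one true detection.

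| True pattern | Bonferroni | Holm | Family-wise error | At least one |
|---|---|---|---|---|
| No differences | – | – | 0.043 / 0.043 | – |
| B and C +25%, D equal to A | 0.80–0.81 | 0.85 | 0.017 / 0.035 | 0.982 for both |
| Only B +25% | 0.81 | 0.83–0.84 | 0.023 / 0.038 | 0.956 for both |
| B, C and D +25% | 0.80–0.81 | 0.83–0.84 | 0.022 / 0.037 | 0.955 for both |
| B +25%, C +56%, D equal to A | 0.80–0.81 | 0.89–0.90 | 0.009 / 0.039 | 1.000 for both |

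In the last pattern C is a further 25% above B (1.25² = 1.56), and the power shown is for A–B, B–C and B–D; A–C and C–D are detected almost always by either method.

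**Step 4: the gain in patients.** In the pattern with B and C raised, Holm's power per comparison is 0.78–0.79 at N = 50 and 0.81 at N = 52. It therefore reaches about 80% at 51–52 patients, against 57 for Bonferroni.

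**The case against.** The strongest reply is that nothing here is wrong. Bonferroni is valid, it was pre-specified, Table 1 was sized at that level, and the promised power for any one pair is delivered. Bonferroni also comes with simultaneous confidence intervals. All of that stands, so the point is about efficiency and not about an error in the design.

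The gain also depends on the pattern, and every power figure rests on a correlation that the plan does not give. At alpha 0.0083, the N for a 25% increase and 80% power runs from 96 at correlation 0 to 39 at correlation 0.6. That uncertainty is larger than the gain from Holm. It does not touch the argument itself, because Holm's advantage over Bonferroni holds at any correlation.

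Three stronger readings are tempting, and the documents do not support them.

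- **That the trial has only about an even chance of success.** A reader might infer from the expected results in Section 3.4 that all four differences (A–B, A–C, B–D, C–D) must be significant. In that pattern the chance is 0.53 with Bonferroni and 0.66 with Holm. But Section 3.4 lists expectations, not a success criterion, and Section 5 sizes a single comparison.
- **That the ANOVA should be used as a gate, so that Shaffer's larger early thresholds apply.** This gives about 0.87 per comparison when B and C are raised. But it does not keep every Bonferroni rejection: one was lost in about 0.7% of simulated trials with no differences and 0.3% with one condition raised. It also makes the pairwise tests depend on an F-test for which the plan specifies no sphericity correction.
- **That the mention of three groups means the alpha or the sample size is wrong.** Step 1 shows that it does not.

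**Conclusion.** The concern holds as an inexpensive improvement to a valid plan. At N = 57, power per true 25% difference rises from about 0.81 to about 0.85 if B and C are raised and A and D are not, to about 0.83 if one condition differs from the rest, and to about 0.90 if C rises further than B. Holm's first threshold is still 0.05/6, so the chance of finding at least one true difference is unchanged.

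The same error control means the same bound. Holm's actual family-wise error is higher when some nulls are true (for example 0.035 against 0.017), but it stays below 0.05.

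That Holm rejects at least as much at the same bound needs no assumption. The sizes rest on CV 0.455 from the plan, the back-solved correlation of about 0.4, equal variances, and two-sided tests on log values. The three-groups wording is a slip that changes no number.

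**What to change.** 1. In Section 5, Statistical Method, replace the flat Bonferroni sentence with: *the six paired comparisons will be tested by Holm's step-down procedure at family-wise 0.05*. Do not make these tests conditional on the ANOVA result. Fix the wording before the data are analysed.
2. Keep 0.0083 as the conservative basis of Table 1, so N = 57 does not change, and for Bonferroni simultaneous confidence intervals reported beside the Holm-adjusted p-values.
3. Under Assumptions, change the description of the overall test from three groups to four conditions.

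The cost is two edited sentences, with no added patients, samples or procedures. The small downside is that Holm has no simple matching intervals. A comparison may then be significant by Holm while its Bonferroni interval includes no difference, and the report should say so where it happens.

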## 6. SAFETY AND ADVERSE EVENTS

### 6.1 Recording of adverse events.

The clinical course of each adverse event will be followed until resolution, stabilization or until it has been determined that the study interventions or participation is not the cause. Serious adverse events that are still ongoing at the end of the study period will be followed up to determine the final outcome. Any serious adverse event that occurs after the study period and is considered to be possibly related to the study treatment or study participation will be recorded and reported immediately.

### 6.2 Reporting of serious adverse events

#### 6.2.1 IRB notification by investigator

1. Adverse events which are serious, unexpected and related or possibly related to participation in the research.

2. Serious adverse events that are expected in some subjects, but are determined to be occurring at a significantly higher frequency or severity that expected.

3. Other unexpected adverse events, regardless of severity, that may alter IRB analysis of the risk versus potential benefit of the research and, as a result, warrant consideration of substantive changes in the researcher protocol or informed consent process/document.

4. Unanticipated problems involving risks to subjects or other or any serious or continuing noncompliance with this policy or the requirements or determinations of the IRB.

### **6.3 Stopping Rules**

In studies with a primary safety endpoint or studies with high risk to study subjects, the circumstances and procedures for interrupting or stopping the study will be clarified. The stopping rules should be incorporated into the data safety analysis plan as well.

### **6.4 Medical Monitoring**

It is the responsibility of the Principal Investigator to oversee the safety of the study at his/her site. This safety monitoring will include careful assessment and appropriate reporting of adverse events as noted above, as well as the construction and implementation of a site data and safety-monitoring plan (see section 8 Auditing, Monitoring and Inspecting). Medical monitoring will include a regular assessment of the number and type of serious adverse events.

## **7. DATA HANDLING AND RECORD KEEPING.**

### **7.1 Confidentiality and Privacy**

Information about study subjects will be kept confidential and managed according to the Health Insurance Portability and Accountability Act of 1996 (HIPAA).

## **7.2 Source Documents**

Source data will include the electronic health record for patient demographics, vitals, and basic laboratory results. Dictated operative notes will be maintained within the EHR as well. Lab results of inflammatory markers will be kept out of the EHR and kept in a secure file on the Cleveland Clinic server.

## **7.3 Records Retention**

The investigators will retain study essential documents for at least six years after completion of the research and are accessible for inspection by authorized representatives at reasonable times and in a reasonable manner.

## **8. STUDY MONITORING, AUDITING AND INSPECTING**

The investigator will permit study-related monitoring, audits, and inspections by the IRB, the sponsor, government regulatory bodies, and Institutional compliance and quality assurance groups of all study related documents (for example, source documents, regulatory documents, data collection instruments, study data etc.). The investigator will ensure the capability for inspections of applicable study-related facilities (for example, pharmacy, diagnostic laboratory, etc.). Participation as an investigator in this study implies acceptance of potential inspection by government regulatory authorities and applicable Institutional compliance and quality assurance offices

## **9.0 ETHICAL CONSIDERATIONS**

This study will be conducted according to US and international standards of Good Clinical Practice (FDA Title 21 part 312 and International Conference on Harmonization guidelines), applicable government regulations and Institutional research policies and procedures.

This protocol and any amendments will be submitted to a properly constituted independent Institutional Review Board (IRB), in agreement with local legal prescriptions, for formal approval of the study conduct. The decision of the IRB concerning the conduct of the study will be made in writing to the investigator and a copy of this decision will be provided to the sponsor [if applicable] before commencement of this study. The investigator should provide a list of IRB members and their affiliate to the sponsor.

All subjects for this study will be provided a consent form describing this study and providing sufficient information for subjects to make an informed decision

## **11. APPENDIX**

### **Optice Nerve Ultrasound**

In the operating room, patients are placed in a supine position and intubated, with both eyes protected by patches. Using an ultrasound with a 12-MHz transducer (General Electric Venue 40, USA), the diameter of the ONS is measured at a standard level of 3 mm from its origin in a single eye. The ultrasound machine is kept in the anesthesia work room and available upon request to the anesthesia technician. Before and after each use the probe is cleaned with alcohol pads. A specific ultrasound probe cover is utilized during contact with the patient's eye lid.
